7.2.1 Efficacy

The endpoints will be compared exploratory between the three groups. No confirmatory statistical tests will be conducted. Primary efficacy analyses will be carried out in an ITT framework using multiple imputed datasets in case of missing values (under the assumption of MCAR or MAR).

7.2.2 Safety/Tolerability

AEs, SAEs, incidents and serious incidents will be -if any occurred- listed per patient and for the total trial.

The safety analysis based on the safety analysis set (according to the patients' received treatment) includes calculation of frequencies and incidence rates as well as incidence rate ratios and corresponding 95% confidence intervals of adverse and serious adverse events using poisson regression or negative binomial regression models depending on the distribution of the variables.

Results of safety analysis will be interpreted and discussed thoroughly also for minor group differences, since statistical significance is not of importance here.

7.2.3 Quality of life

Quality of life is assumed to be linked with patient satisfaction and the interview part. There is no specific separate questionnaire.

7.3 Planned subgroup analyses

Differential treatment effects will be analyzed by including interaction terms for subgroups by intervention group. Prespecified subgroups include sex (male/female) and patients with and without IAD 1A status at baseline. For the subgroup consisting of no initial IAD, a second time-to-event analysis will be realized, using the first occurrence of any IAD category as event and thus including 1A and 1B. Additionally, location (front/back) of IAD and Erosion will be considered for subgroup analyses as well. Parallel to interaction effects estimated marginal treatment effects of the subgroups and 95% CI will be reported.

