2.2.2 RESIDENT/PATIENT LEVEL

Inclusion criteria:

Geriatric patients (≥ 65 years) admitted to geriatric wards of participating hospitals or residents of participating nursing homes can be included if the following criteria are met:

- (1) Being incontinent of urine and stool
- (2) Expected minimum length of stay of 14 days
- (3) Intact skin with no clinical signs of IAD

OR

Intact skin with early clinical signs of IAD (erythema) but without clinical signs of infection (GLOBIAD category 1 A)

- (4) Written informed consent (by legal representative, if required)

Exclusion criteria:

- (1) Residents/patients at the end of life
- (2) Residents/Patients with skin loss due to IAD (GLOBIAD category 2 A) and/or signs of clinical infection in the IAD area (GLOBIAD category 1 B, category 2 B)
- (3) Any other skin condition or wounds (at investigational areas of the skin) requiring additional treatment (including but not limited to pressure ulcers, intertrigo, infection)
- (4) Known hypersensitivity or allergy to silicones and/or topical leave-on products
- (5) Topical treatments in the IAD area.

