2.7 OUTCOMES AND VARIABLES

Because of the exploratory nature of the trial and according to methodological guidance for exploratory trials, a distinction between primary and secondary endpoints is not made [23]. Because the main aim is to prevent IAD, IAD incidence is likely to be considered as a primary outcome in a possible subsequent confirmatory trial.

Table 2: Outcomes and variables per participant

Outcome Name	Device/Measurement instrument/Scale and metric	Time points	Response Options/Categories/ Range
IAD incidence	
 • IAD Classification according to GLOBIAD [24] and distinction between intact and eroded skin according to Proceedings of the Global IAD Expert Panel [10] • Cumulative incidence • IAD Localization according to the following definition: 
 ○ Back: Sacral region going down to the upper thighs, bordered approximately 5 cm below the gluteal fold ○ Front: Navel to upper thigh 	Days 0, 2, 4, 6, 8, 10, 12, 14	
 • Presence of IAD: 
 (1) None; (2) Category 1 A; (3) Category 1 B; (4) Category 2 A; (5) Category 2 B • Localization of IAD: 
 (1) Back (2) Front
Erythema	
 • Rating according to the item 'Redness' of the incontinence-associated dermatitis and its severity (IADS) instrument [25] • 3-Item-Scale (ordinal) 	Days 0, 2, 4, 6, 8, 10, 12, 14	
 • Redness: 
 (1) None; (2) Pink; (3) Red/Bright red

Outcome Name	Device/Measurement instrument/Scale and metric	Time points	Response Options/Categories/ Range
	
 • Mexameter MX18 with MDD 4 (Courage + Khazaka Electronic GmbH) [26] (measurements according to SOP „Mexameter® MX 18“ Version 1.0, 18.05.2022) (see Fehler! Verweisquelle konnte nicht gefunden werden.) • Arbitrary units (AU) from 0 (= no erythema) to 999 (= extreme erythema) • Means of duplicate measurements at the cranial end of the gluteal cleft 	Days 0, 2, 4, 6, 8, 10, 12, 14	
 • Erythema level: 0 - 999 [numeric; AU]

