Intervention therapy:	Intervention arm I: Standardized mild skin cleansing regimen and daily topical application of a film-forming skin protectant at the exposed skin areas. Intervention arm II: Standardized mild skin cleansing regimen and daily topical application of a hydrophobic skin protectant at the exposed skin areas.
Control therapy:	Standardized mild skin cleansing regimen without application of an additional skin protectant
Study population:	Incontinent geriatric patients
Sponsor:	Charité - Universitätsmedizin Berlin, [name]
Financial support:	Federal Ministry of Education and Research (Bundesministerium für Bildung und Forschung (BMBF)) by grant number 01KG2020.
Protocol registry identification:	DRKS00028954
Clinical phase:	Randomized controlled, parallel group, three-arm, assessor-blinded exploratory trial

Approved by

[name]. rer. cur. [name]
Name, Principal Investigator

Place, Date, Signature

Dipl.-Math. [name]
Name, Statistician

Place, Date, Signature

PD Dr. phil. [name]
Name, Statistician

Place, Date, Signature

Dr. rer. medic. [name]
Name, Trial Coordinator

Place, Date, Signature

File history

Version	Date	Major changes	Comment
01	01/14/2025		Initial SAP
02	03/20/2025	
 Erythema level 1 and 2 reporting Exclusion of feasibility assessment Analysis of erosion: no adjustment for baseline Correction of cognitive condition for patient satisfaction assessment Specification of timepoints for secondary outcome assessments Addition of location (front/back) for subgroup analyses 	
The mean of Erythema levels 1 and 2 will be aggregated and analyzed as endpoint
 
The percentage of eligible individuals who were willing to participate could not be assessed.
 
Erosion at baseline was exclusion criterion
 
If IAD present and MMSE ≥ 24
 
If IAD present
 
For Erosion
 
Remark: additional minor changes (formatting, spelling and grammar)

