7.2 Analyses of endpoints

Because of the exploratory nature of the trial and according to methodological guidance for exploratory trials, a distinction between primary and secondary endpoints is not made [23]. Because the main aim is to prevent IAD, IAD incidence is likely to be considered as a primary outcome in a possible subsequent confirmatory trial and is therefore considered as primary efficacy variable.

For all outcomes, total group differences are reported by the corresponding effect size based on the statistical models as outlines below and corresponding 95% confidence intervals. Relevant timepoints will be Day 6 and Day14. Day0 reports will be presented as is.

The relevant blinded group comparisons are: A vs. B; A vs. C; B vs. C.

For cumulative incidence rates of IAD, Kaplan-Meier Curves will be presented with time ranging from inclusion to IAD onset, i.e. the first occurrence of IAD 2A or 2B. Censoring occurs if patients withdraw from the study before the onset of an IAD or if the study is terminated before IAD onset. Mixed effects Cox regression model (shared frailty model) will be carried out for group comparisons of incidence rates. The latter includes group allocation, sex, setting (nursery home, geriatric hospital ward) and time (continuous) as fixed effects and random intercepts for the ward and the patients. The resulting Hazard ratios for IAD will be presented. Potential non-linear time effects will be explored and modelled using fractional polynomials or splines.

Group differences for categorical, dichotomous responses are calculated by estimating group effects from either generalized linear mixed-effects models (binary logistic) - including particular baseline status (maceration, IAD-related itch), group allocation, sex, setting and time as fixed effects and random intercepts per ward and patients - or nonparametric analysis of longitudinal data depending on the distribution of the data. For the Erosion model, no baseline adjustment is considered due to its presence is an exclusion criterion.

List:

- Erosion (no/ yes)
- Maceration (no/ yes)
- IAD related itch (no/ yes) [only measured if IAD present]
- IAD-related pain (no/yes) [only measured if IAD present]

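### SAP 7.3 uses lesion location (front/back) as a subgroup without tying it to baseline: not estimable for erosion, biased for IAD that arises after Day 0

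*Combined protocol and SAP*

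**What the plan says.** SAP 7.3 (Planned subgroup analyses) sets the method first: "Differential treatment effects will be analyzed by including interaction terms for subgroups by intervention group". It then names two subgroups: "Prespecified subgroups include sex (male/female) and patients with and without IAD 1A status at baseline". Location follows in its own sentence: "Additionally, location (front/back) of IAD and Erosion will be considered for subgroup analyses as well". The section closes with the output: "Parallel to interaction effects estimated marginal treatment effects of the subgroups and 95% CI will be reported". The SAP file history, version 02, records "Addition of location (front/back) for subgroup analyses", with a comment that links it to erosion.

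Four other places matter:

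- **Entry with IAD.** Protocol 2.2.2 admits participants with "Intact skin with early clinical signs of IAD (erythema) but without clinical signs of infection (GLOBIAD category 1 A". It excludes those with skin loss due to IAD.
- **Entry with erosion.** SAP 7.2 drops baseline adjustment from the erosion model because erosion is an exclusion criterion.
- **Recording of location.** Protocol Table 2 places location within the IAD outcome ("IAD Localization according to the following definition") and schedules it from Day 0 to Day 14. SAP 4.2 holds front and back as separate yes/no items for IAD (skin_0015, skin_0016) and for erosion (skin_0044, skin_0045). None of the four carries the Day 0 mark that the SAP uses for baseline data.
- **Main event.** SAP 7.2 defines IAD onset for the Kaplan-Meier curves as "i.e. the first occurrence of IAD 2A or 2B". SAP 7.3 adds a second time-to-event analysis, with any IAD category as the event, in those without IAD at entry.

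**The concern.** A subgroup for a treatment effect has to be fixed by randomisation or unaffected by treatment. Sex and baseline 1A status meet this; lesion location at an unstated visit need not. If membership requires the outcome, the between-arm contrast inside the subgroup has nothing to estimate. If membership requires an earlier step towards the outcome, the arms inside the subgroup are no longer the randomised arms.

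The trial is meant to supply effect sizes for a confirmatory trial. A spurious finding that a product works at one site and not the other, printed with 95% intervals and without multiplicity adjustment, could mislead that design.

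**Working it through.** The plan gives no figure for this analysis, so there is none to reproduce. The argument takes each kind of location in turn.

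**1. Erosion location.** Nobody has an erosion at Day 0, so nobody has an erosion location at randomisation. Membership of an erosion-front or erosion-back subgroup implies an on-study erosion. The risk of ever eroding is therefore 1.000 in every arm, the risk ratio is 1.00 and the risk difference is 0, whatever the treatment does. Coding lesion-free participants as 'no' does not help: the 'yes' level still consists of cases only.

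**2. IAD location in participants free of IAD at Day 0.** They acquire a location only by developing IAD. For the any-IAD analysis in SAP 7.3, each such member is a case, as in step 1. For the 2A/2B event they are not all cases, but they are selected on a variable that treatment can change.

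The size depends on rates that the documents do not give. The following inputs are assumptions for illustration:

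- Frailty U is uniform on 0 to 1. New IAD has risk 0.6U in control (mean 0.30), halved by treatment (mean 0.15).
- Progression to category 2 has risk 0.8U once IAD is present (mean 0.40 in baseline-1A participants), with no treatment effect.
- Location is 60% back only, 20% front only and 20% both, so 80% involve the back.
- The baseline 1A share p is 20% or 50%.

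In those without IAD at Day 0, the control risk of 2A/2B is E[0.6U × 0.8U] = 0.48 × 1/3 = 0.16. The treated risk is 0.08, so the true risk ratio is 0.50. Among those of them who later have IAD at the back, the risks are 0.16/0.30 = 0.533 and 0.08/0.15 = 0.533, a risk ratio of 1.00. The preventive effect has vanished.

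**3. IAD location at any visit, all participants.** The formulas are:

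- 2A/2B risk, all randomised: 0.40p + 0.16(1 − p) in control; 0.40p + 0.08(1 − p) in treated.
- Share ever having IAD: p + 0.30(1 − p) in control; p + 0.15(1 − p) in treated. Multiply by 0.8 for the back.
- Risk within the back subgroup: the first line divided by the share ever having IAD.

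| p | 2A/2B risk, treated vs control | Risk ratio, all randomised | Back-subgroup share, treated vs control | Risk within back subgroup, treated vs control | Risk ratio, back subgroup |
|---|---|---|---|---|---|
| 20% | 0.144 vs 0.208 | 0.69 | 25.6% vs 35.2% | 0.450 vs 0.473 | 0.95 |
| 50% | 0.240 vs 0.280 | 0.86 | 46.0% vs 52.0% | 0.417 vs 0.431 | 0.97 |

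Unequal shares show that treatment changes who is in the subgroup. A simulation of 1,000,000 per arm agrees with these values to within 0.01. When treatment also halves progression, the simulated risk ratio in all randomised participants is 0.35 (p = 20%) or 0.43 (p = 50%), against 0.48 in the back subgroup.

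**4. IAD location at Day 0 in baseline-1A participants.** Here location precedes randomisation and the 2A/2B event. In the simulation the arms have equal shares in this subgroup, and the risk ratio is 1.00 without an effect on progression and 0.50 with one, as put in. There is no bias. Of 70 per arm, the stratum holds 70 × 0.20 = 14 to 70 × 0.50 = 35 participants before any front/back split. The remaining 50% to 80% have no location at Day 0.

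**5. Overlap.** Under the assumed location split, back (80%) plus front (40%) sums to 120%. The two groups are not exclusive, and SAP 7.3 does not say how participants with both sites, or with neither, are classified.

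**The case against.** The strongest reply is that the location sentence means site-specific outcomes: front and back lesions analysed separately in everyone. It stands apart from the sentence on prespecified subgroups, the file-history comment ties it to erosion, and SAP 4.2 lists front and back as separate items to be reported as counts and percentages. That analysis would be sound. The reading is possible, but it is not what the text says: the heading, the linking words and the promise of effects per subgroup all place location under the interaction method. If site-specific outcomes were meant, the same edit is needed.

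A second reply is that SAP 7.2 models erosion over repeated visits, so a participant who erodes once need not be positive at every visit. This stands, but a model restricted to such participants describes timing or persistence among cases, not prevention of erosion.

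A third is that the analysis is exploratory, was added late and leaves the main comparison untouched. This is true, and it limits the importance of the point. It does not make an inestimable contrast informative.

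Stronger readings also need to be set aside. A reader might infer that location exists only after the outcome, so that every analysis by location is invalid. The documents do not support that: category 1A is allowed at entry, location is scheduled on Day 0, and the main event is 2A/2B. Nor is the risk 100% for 2A/2B among participants with an IAD location, since they may have only 1A or 1B. Finally, the 35.4% prevalence in the background section cannot serve as the baseline 1A share. It counts any form of IAD among residents of long-term care facilities, whereas this trial requires incontinence of both urine and stool and excludes 1B, 2A and 2B.

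**Conclusion.** The point holds in a limited form. As written, SAP 7.3 makes location a treatment-effect subgroup with no link to baseline.

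- **Erosion location:** no arm contrast or interaction on erosion occurrence can be estimated. This follows from the eligibility criteria alone and needs no assumed rates.
- **IAD location arising after Day 0:** the subgroup is selected on a treatment-affected variable and its effect estimate is biased. For the any-IAD analysis every such member is a case. The direction and size for 2A/2B rest on the assumed rates above.
- **Day 0 IAD location in baseline-1A participants:** a valid subgroup, limited to a stratum whose share the documents do not give.

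The coding of both sites and of no lesion is also undefined. The change should be made before the subgroup results are produced, but it has no bearing on the main comparison of IAD incidence.

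**What to change.** In SAP 7.3, remove erosion location and post-baseline IAD location from the subgroup list. In SAP 7.2, add front and back as site-specific binary outcomes in all participants of the full analysis set:

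- Code each site yes/no at each visit, with 'no' when the lesion is absent rather than missing or not applicable.
- Fit a logistic mixed model with arm, site and arm-by-site terms and a patient random effect, alongside the covariates and ward effect already in SAP 7.2. Report the arm contrasts for front and back separately.
- For IAD, adjust for presence at that site on Day 0. Erosion needs no such term.
- Use skin_0044/0045 for erosion, skin_0015/0016 for any IAD, and the GLOBIAD categories skin_0012/0017 for site-specific 2A/2B.

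Optionally, keep Day 0 IAD location as a subgroup within the baseline-1A stratum only, and state how participants with both sites are classified.

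The cost is SAP wording and some extra modelling; no new data are needed. If front-site events are sparse, their intervals may be wide.

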7.4 Interim analyses

No interim analyses are planned in this study.

8 Software

We will use the data management software REDCap for data handling and storage, as well as the open source software R for all analysis steps in version 4.2.0 or greater.

9 References

- [3] Van Damme N, Van den Bussche K, De Meyer D, Van Hecke A, Verhaeghe S, Beeckman D. Independent risk factors for the development of skin erosion due to incontinence (incontinence-associated dermatitis category 2) in nursing home residents: results from a multivariate binary regression analysis. *Int Wound J.* 2017;14:801-10.10.1111/iwj.12699.
- [10] Beeckman D. Proceedings of the Global IAD Expert Panel. Incontinence-associated Dermatitis: moving prevention forward. London: Wounds International; 2015.

10.1 Program code

The statistical code for analysis of the endpoints will be made available on drks.de

10.2 Exemplary table layouts

Table 1: PID - Demographics

Characteristic	Overall N =	Group A, N =	Group B, N =	Group C, N =
Age				
Mean (SD)	x.xx (x.xx)	x.xx (x.xx)	x.xx (x.xx)	x.xx (x.xx)
Median [IQR]	x.xx [x.xx; x.xx]	x.xx [x.xx; x.xx]	x.xx [x.xx; x.xx]	x.xx [x.xx; x.xx]
(Minimum,Maximum)	(x.xx, x.xx)	(x.xx, x.xx)	(x.xx, x.xx)	(x.xx, x.xx)
Sex, n (%)				
Female	x (pp.p)	x (pp.p)	x (pp.p)	x (pp.p)
Ward setting, n (%)				
Geriatric hospital	x (pp.p)	x (pp.p)	x (pp.p)	x (pp.p)
Nursing ward	x (pp.p)	x (pp.p)	x (pp.p)	x (pp.p)

Table 2: PID – IAD incidence characteristics: Hazard Ratios

Predictors	Hazard Ratio	95% CI
Study arm		
A	-	-
B	x.xx	x.xx to x.xx
C	x.xx	x.xx to x.xx
Sex		
Female	-	-
Male	x.xx	x.xx to x.xx

Table 3: PID – Secondary outcome characteristics

Outcome	Contrast	Estimate	Effect size	95% CI
Maceration				
	A vs. B	x.xx	x.xx ^a	x.xx to x.xx
	A vs. C	x.xx	x.xx ^a	x.xx to x.xx
	B vs. C	x.xx	x.xx ^a	x.xx to x.xx
Erythema level				
	A vs. B	x.xx	x.xx ^b	x.xx to x.xx
	A vs. C	x.xx	x.xx ^b	x.xx to x.xx
	B vs. C	x.xx	x.xx ^b	x.xx to x.xx

a) Odds Ratio; b) Cohen’s d
